#### **4.3. Additional exclusions from PP analysis**

1. Patients lost to follow-up or withdrawn before the end of treatment, unless they have already been classified as having an unfavourable outcome.

2. Patients whose treatment was modified or extended for reasons (e.g. an adverse drug reaction or pregnancy) other than an unfavourable therapeutic response to treatment, unless they have already been classified as having an unfavourable outcome.

3. Patients not meeting the definition of having received an adequate amount of their allocated study regimen (see section 4.5 for definition), provided they have not already been classified as having an unfavourable outcome.

4. Patients who are classified as “major protocol deviations” (see below), unless they have already been classified as having an unfavourable outcome on the basis of data obtained prior to the protocol deviation.

A list of all protocol deviations will be compiled throughout the course of the study.

A **Major Protocol Deviation** is defined as a serious protocol deviation which is likely to affect to a significant degree the safety or physical or mental integrity of the subjects of the trial or the scientific value of the trial. These patients will be included in the ITT and MITT analyses, but not in the Per Protocol analysis. A list of all major protocol deviations will be approved by the study Coordinating Investigator before database lock.

A **Minor Protocol Deviation** is defined as a technical deviation which does not result in harm to the trial subjects or significantly affect the scientific value of the reported results of the trial.

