## 1. Introduction

This document outlines the efficacy statistical analysis plan (SAP) for the protocol STAND, a phase 3 trial of three experimental regimens of the combination regimen of moxifloxacin, PA-824 and pyrazinamide (MPaZ).

The primary efficacy analysis will be conducted using culture results from liquid culture (MGIT) and will evaluate the hypothesis that in the patients with drug-sensitive tuberculosis (DS-TB) treated with any of the experimental MPaZ regimens, the incidence of bacteriologic failure or relapse or clinical failure at 12 months from the start of therapy is non-inferior to the proportion observed in patients who are treated with the 6 month standard isoniazid, rifampicin, pyrazinamide, ethambutol (HRZE/HR) regimen.

The three experimental regimens detailed below will be compared to the control regimen in the order specified. For the second and third comparison, statistical inference will only be made if non-inferiority is declared on the preceding comparison:

*First comparison:* MPaZ with 200mg PA-824 (MPa200Z) for 6 months vs HRZE/HR

*Second comparison:* MPaZ with 200mg PA-824 (MPa200Z) for 4 months vs HRZE/HR

*Third comparison:* MPaZ with 100mg PA-824 (MPa100Z) for 4 months vs HRZE/HR

300 patients per randomised arm will be recruited. See Appendix 1 for details of the sample size. An additional non-randomised group of up to 300 patients with multi-drug resistant (MDR) TB will be treated with regimen MPa200Z for 6 months. No formal statistical analysis is planned for this group and unless otherwise stated all analyses outlined in this document refer to the analysis of the 4 randomised groups of the DS-TB patients.

While STAND is an open label study, only members of the Data Safety Monitoring Committee (DSMC) and the unblinded statistician(s) will have access to data **grouped by study arm**. Access to data by investigators, CRO and TB Alliance staff will not allow any access to data grouped by study arm. In addition, site staff will be strongly discouraged from attempting to aggregate by treatment arm at a site level.

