#### **4.6. Determining cause of death**

A list of all ***TB-related*** and ***non-TB-related deaths*** will be generated and approved by a review committee **blind to randomised arm** before database lock. Similarly a list of violent or accidental deaths will be generated.

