## **7. Determination of statistical non-inferiority**

The first comparison to be tested will be the MPa200Z 6 month experimental regimen against the standard regimen. The second comparison to be tested will be the MPa200Z 4 month experimental regimen against the standard regimen. The third comparison to be tested will be the MPa100Z 4 month experimental regimen against the standard regimen. To preserve the type I error rate, the second comparison will only be tested if non-inferiority is demonstrated with the 6 month experimental regimen. Similarly the third hypothesis will only be tested if non-inferiority of the PA-824 200mg 4 month regimen has been demonstrated. This strategy means no adjustments are required for multiple comparisons.

Non-inferiority will be assessed using the upper bound of the two-sided 95% confidence interval for the difference between the proportion of participants who are classified as having an unfavourable status on the intervention and the control regimen.

If the upper bound of the two-sided 95% confidence limit for the difference, proportion with unfavourable status on intervention arm less the proportion with unfavourable outcome on the control arm, is less than 12% (the margin of non-inferiority) the intervention will be considered to be non-inferior to the control arm on that comparison.

The PP and MITT analyses will be considered primary. However, in order to declare an intervention to be non-inferior, consistent results should be obtained from the ITT analysis and from sensitivity and subgroup analyses, although not all of these will necessarily satisfy the strict definition of non-inferiority.

All primary efficacy analyses of the three main analysis populations will be adjusted for HIV status and cavitation, using a stratified analysis of the risk difference from each stratum using Cochran-Mantel-Haenszel weights.

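### SAP 4.3 does not require the approver of the major-deviation list, one of four additional PP exclusions, to be blind to arm or outcome, although the trial is open label and PP is one of two primary analyses

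*SAP*

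**What the plan says.** Section 4.3 of the SAP adds four exclusions to the MITT exclusions to form the PP population. The fourth is for major protocol deviations.

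- **Definition.** A deviation is major if it is serious and "likely to affect to a significant degree the safety or physical or mental integrity of the subjects of the trial or the scientific value". No deviation types are listed.
- **Approval.** All deviations are logged as the study proceeds. For the major ones, "A list of all major protocol deviations will be approved by the study Coordinating Investigator before database lock".
- **Effect.** "These patients will be included in the ITT and MITT analyses, but not in the Per Protocol analysis".
- **Protection of events.** A patient with a major deviation is excluded from PP "unless they have already been classified as having an unfavourable outcome on the basis of data obtained prior to the protocol deviation".

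Section 7 gives the weight of this population: "The PP and MITT analyses will be considered primary". Section 1 states that the trial is open label and denies investigators, CRO and sponsor staff any data grouped by arm. Section 4.6 covers TB-related and non-TB-related deaths: that list "will be generated and approved by a review committee" blind to randomised arm, also before database lock.

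**The concern.** Four features combine. The grading is a judgement, one person approves it, allocation is not concealed in an open-label trial, and the grading can remove an event from a primary analysis. Exclusions 1 to 3 in section 4.3 keep any patient already classified as unfavourable. Exclusion 4 is narrower: the unfavourable classification must rest on data from before the deviation. A patient who deviates and later fails or relapses therefore leaves PP if the deviation is graded major and stays if it is graded minor.

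Approval has to come before database lock but need not come before outcomes are known. If the approver knows a patient's arm or result, the grading can be influenced by it, even without intent. In a non-inferiority comparison, losing a few experimental-arm failures moves the PP result towards a pass. Under the fixed testing order in section 7, a pass on one comparison also opens the next.

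**Working it through.** **1. The passages compared.**

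- Deaths (4.6): approved by a committee, before lock, blind to arm.
- Major deviations (4.3): approved by one investigator, before lock; blinding not mentioned.
- General rule (1): no arm-grouped data for investigators. An individual patient's allocation is not addressed.

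No other section of the SAP masks the deviation review. The authors did not treat the general rule as enough for deaths, where they added explicit blinding, or for cavitation, where sections 5 and 11 specify a blinded central reading.

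**2. The plan's own design figure.** Inputs from Appendix 1: 16% unfavourable on control (the same rate assumed on the experimental arm), margin 12%, one-sided 2.5%, power 90%, 15% unassessable, 8% INH mono-resistant.

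n = 2 × 0.16 × 0.84 × (1.960 + 1.282)² / 0.12² = 196.1 evaluable per arm

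196.1 / (1 − 0.15 − 0.08) = 254.7, against 255 stated. The figure reproduces, and nothing in this point changes it.

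**3. How few exclusions matter for PP.** The unadjusted 95% upper bound is

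U = (pE − pC) + 1.96 × √[pE(1 − pE)/nE + pC(1 − pC)/nC],

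and the comparison passes if U < 12%. The event counts are assumed. A control rate of 5% is the top of the 3% to 5% range that section 2 expects for true bacteriologic failure and relapse.

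| Experimental | Control | Difference + half-width | U | Result |
|---|---|---|---|---|
| 25/200 | 10/200 | 7.5 + 5.5 | 13.0% | fail |
| 23/198 (two removed) | 10/200 | 6.6 + 5.4 | 12.01% | fail, just |
| 22/197 (three removed) | 10/200 | 6.2 + 5.3 | 11.5% | pass |

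Table A1 gives 6.0% as the largest passing difference for 200 per arm and 5% on control, without naming its method. By that figure three removals (11.2 − 5.0 = 6.2%) are not quite enough, and four are: 21/196 = 10.7%, a difference of 5.7%. The number needed remains small.

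At the plan's 16% control rate:

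- 197 per arm, 32 control events: 40 experimental events pass (11.7%) and 41 fail (12.2%). Removing one gives 40/196 and 11.8%, a pass. From 43 events it takes four removals (11.6%).
- 231 per arm (300 × 0.77), 37 control events: 48 pass (11.8%) and 49 fail (12.3%). Removing one gives 11.9%, a pass.

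Further from the margin the lever weakens: with 197 per arm, a result of 47 experimental events needs nine removals.

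**4. What happens in MITT.** The removed failures stay in MITT.

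- If MITT were the same 200 per arm, it would remain at 13.0% and fail.
- Suppose MITT has 31 more patients per arm (231, assumed) with equal numbers of added unfavourable outcomes in each arm. U is then 11.3% with 0 added, 11.9% with 5, 12.4% with 10 and 13.2% with 20.
- Suppose instead that early losses, which are unfavourable in MITT and excluded from PP (4.4), number 10 on the experimental arm and 15 on control. MITT is then 35/210 against 25/215, U = 11.7%, a pass. PP at 25/200 against 10/200 fails, so the gradings would settle the one failing primary analysis.

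**The case against.** The strongest objection is that PP does not decide the trial alone. MITT is equally primary, section 7 asks for consistent ITT results before non-inferiority is declared, and the excluded patients remain in both. A reader might infer from 13.0% falling to 11.5% that the trial's conclusion would change. The documents do not support that: it is a change in PP only, and step 4 shows MITT often still failing. What remains is the case in which MITT passes and PP does not. The SAP does not say outright that both must pass, but it calls both primary.

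A reader might also infer that the approver is unblinded, or grades deviations at the end with outcomes in view. The SAP says neither. It is silent on blinding, and it has deviations logged throughout the study, which makes it harder to find deviations after the event. The major or minor grading is still a judgement that need only be approved before lock.

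Section 1 is a partial answer. A cross-site listing that showed each patient's arm could be grouped by arm at once, so supplying one would defeat that rule. Knowledge of individual allocations, for instance at the approver's own site, is not covered.

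The comparison with deaths is imperfect. Cause of death affects both MITT and PP, while deviations affect PP only, so stronger protection for deaths is defensible. Finally, the protocol is not at hand and may add a blinded review. But section 4.3 itself sets out who approves the list and when, so the procedure is not simply left to the protocol.

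**Conclusion.** The point stands as a gap in a stated procedure. Section 4.3 names the approver and the deadline for a judgement-based list that can remove later failures from a primary analysis of an open-label trial, and it does not require blinding to arm or outcome. Section 4.6 shows that the authors had the arm-blind safeguard available.

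In size, one to four discretionary exclusions can turn a near-margin PP failure into a pass. This rests on assumed event counts and an unadjusted Wald bound; the planned analysis is stratified by HIV status and cavitation and would give somewhat different bounds. It also requires that the excluded patients are experimental-arm failures arising after the deviation.

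The point should not be read as saying that the list alone defines PP (it is one of four additional exclusions), that bias is expected, or that the overall conclusion would turn on it. MITT and ITT keep these patients and limit the effect. It is a modest weakness with a cheap remedy.

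**What to change.** Amend section 4.3 to state that the major-deviation list is approved before database lock by reviewers blind to randomised arm, for example the committee described in section 4.6. Add that the listings they work from omit the 12-month outcome. This second requirement is new, because section 4.6 blinds its committee to arm but says nothing about outcome.

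The cost is a sentence or two in the SAP and the preparation of masked listings. Masking will be incomplete: some deviations reveal the regimen by their nature, and those fields can be masked only where possible. No sample-size figure or analysis method changes.

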#### **4.4. Lost to Follow-up or Early Withdrawal**

Lost to Follow-up or Early Withdrawals *before* the end of the treatment (month 4 or 6) are considered as unfavourable outcomes for ITT and MITT. However these patients will be excluded from the Per Protocol analysis. The MITT and Per Protocol analyses will consider Lost to Follow-up *after* end of treatment (month 4 and 6) as unassessable unless at the time of default from follow-up the patient a) was already classified as having an unfavourable outcome, b) did not have culture negative status, or c) had a positive culture result (“isolated positive culture”) not followed by at least two negative culture results at different visits (at least 7 days apart), in which cases the patient will be classified as having an unfavourable outcome. We believe this is the most appropriate approach for the primary analysis because together with the non-tuberculosis deaths, this group is likely to considerably out-number the bacteriological failures and relapses. These patients will be considered as having an unfavourable outcome in the ITT analysis.

There is a clear precedent for this analytic approach in other TB trials, and these trials also provide examples of why the inclusion of the losses to follow-up as unfavourable greatly affects the results.

Data from the Priftin trial which led to accelerated approval of rifapentine and a trial conducted by the International Union Against TB & Lung Disease (IUATLD) in African and Asian sites illustrate the problems associated with classifying all losses to follow-up and deaths as having an unfavourable outcome.

In the Priftin trial bacteriological relapses occurred in 5% of patients on the rifampicin based regimen compared to 11% on the rifapentine based regimen. Approximately one third of patients were lost to follow-up and when this group combined with patients unassessable for other reasons were added to the bacteriological failures, the rates increased to 53% and 57% respectively. The true bacteriological relapses were greatly outnumbered by these other groups. At the time of the licensing submission to the FDA it was recognised that because there were a substantial number of patients likely to be unassessable the main focus should be on the relapse rates. In the final statistical report the results were first reported excluding those unassessable and then assuming all losses had an unfavourable outcome and finally assuming all losses had a favourable outcome.

In the study conducted by the IUATLD the published failure/relapse rates 12 months after stopping treatment based on 1044 assessable patients were 4% for the control regimen and 10% and 14% in each of the experimental arms. If the 311 unassessable patients were considered to have an unfavourable outcome these rates would increase to 24%, 32% and 35% respectively. The 311 unassessable patients were not evenly distributed across the three trial arms. There were 42 deaths, of which 20 occurred in one of the experimental arms (the more efficacious of the two) and 11 in each of the other, a difference which was not considered to be due to the treatment, but due to chance. There were also imbalances among those without a bacteriological assessment (7 in one arm versus 19 and 22 in the other two arms) and in the distribution of losses to follow-up.

#### **4.5. Definition of adequate treatment**

The definition of adequate treatment sets a limit for the amount of treatment missed. Patients not taking the adequate amount of treatment by this definition will be excluded from the PP analysis.

For patients allocated to a 6 month regimen, to meet the definition of adequate treatment they must have taken at least 146 doses (80%) of their allocated 182 day (26 weeks) treatment regimen within 203 days of starting therapy (i.e. 26 weeks plus an allowable 3 weeks extension ).

For patients allocated to a 4 month regimen, to meet the definition of adequate treatment they must have taken at least 96 doses (80%) of their allocated 119 day (17 weeks) treatment regimen within 140 days of starting therapy (i.e. 17 weeks plus an allowable 3 weeks extension ).

Patients in the control arm are additionally required to have taken at least 80% of their allocated intensive treatment.

#### **4.6. Determining cause of death**

A list of all ***TB-related*** and ***non-TB-related deaths*** will be generated and approved by a review committee **blind to randomised arm** before database lock. Similarly a list of violent or accidental deaths will be generated.

## **5. Baseline comparisons of key characteristics**

The following baseline characteristics of patients on each of the five study arms (including the non-randomised MDR group) will be tabulated and compared for each analysis population: age, gender, race, region, site, smoking status, HIV status/CD4 count, cavitation (based on blinded, central assessment of the chest radiograph (refer to Central Chest X-ray Manual), initial bacterial load in sputum as indicated by baseline Time to Positivity (TTP) result from MGIT, resistance to first and second line antibiotics and whether or not the patient is taking efavirenz.

## **6. Classification of primary endpoint status**

Patients will be classified as having a favourable, unfavourable or unassessable status at 12 months from the start of therapy.

### **6.1.1. Favourable status (all analyses)**

Patients with a negative culture status at 12 months from start of therapy (from 50 weeks to 54 weeks), who had not already been classified as having an unfavourable outcome, and whose last positive culture result ("isolated positive culture") was followed by at least two negative culture results.

### **6.1.2. Unfavourable status in ITT population**

Patients in the ITT analysis population who do not have a favourable outcome by 12 months will be considered to have an unfavourable response in the ITT analysis.

### **6.1.3. Unfavourable status in MITT population**

1. Patients not classified as having achieved or maintained culture negative status when last seen, or
2. Patients previously classified as having culture negative status who, following the end of treatment, have two positive cultures without an intervening negative culture, (however, see Section 3.3 for an exception), or
3. Patients who had a positive culture not followed by at least two negative cultures when last seen, or
4. Patients dying from any cause during treatment, except from violent or accidental cause (e.g. road traffic accident), not including suicide (eg, suicide will be considered an unfavourable outcome) or
5. Patients definitely or possibly dying from TB related cause during the follow-up phase or
6. Patients requiring an extension of their treatment beyond that permitted by the protocol, a restart or a change of treatment for any reason except reinfection or pregnancy, or
7. Patients failing to complete an adequate course of treatment, as defined in section 4.5, who were unassessable at 12 months, or
8. Patients lost to follow up or withdrawn from the study before the end of treatment

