**Relapse or Bacteriologic relapse** is defined as failing to maintain culture negative status or being declared an unfavourable outcome after the end of treatment (either 4 or 6 months) in those patients who attained culture negative status by the end of treatment, and were re-infected with the **same** (as per the STAND Laboratory Manual) *Mycobacterium tuberculosis (MTB)* strain.

**Reinfection or Bacteriologic Reinfection** is defined as failing to maintain culture negative status or being declared an unfavourable outcome after the end of treatment (either 4 or 6 months) in those patients who attained culture negative status by the end of treatment and were infected with a *Mycobacterium tuberculosis (MTB)* strain that is **different** (as per the STAND Laboratory Manual) from the infecting strain at baseline.

**Clinical failure** is defined as a change from protocol-specified TB treatment or retreatment for TB during follow up as determined by the treating physician, or TB-related death.

The **treatment period** is defined as either 4 or 6 months from start of therapy depending on allocated treatment regimen and the **follow-up period** is defined as the period after the end of treatment to the end of follow-up.

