### 3.4. Timing of events

In all analyses, visit date rather than day or week number will be used to define the timing of events. The 4 month regimens will be taken as 17 weeks (119 days) and the 6 month regimens as 26 weeks (182 days) from the start of therapy. For the end of treatment visit (months 4/6), a  $\pm 1$  week window will be applied (as per the protocol). For the 12 and 24 month visits, a window of  $\pm 2$  weeks will be applied (as per the protocol).

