## 4. Analysis populations

The analysis populations for efficacy analyses are:

- The **All Randomised** population defined as all patients randomised with no exclusions
- The **Intent to treat (ITT)** population is defined as All Randomised excluding late screening failures (see 4.1)
- The **Modified intent to treat (MITT)** population is defined as the ITT population with extra exclusions (See 4.2)
- The **Per-protocol (PP)** population is defined as the MITT population with extra exclusions (see 4.3)

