#### **4.2. Additional exclusions from MITT analysis**

1. Patients who, having completed treatment, are lost to follow-up or withdrawn from the study, their last status being culture negative and their last positive culture result (“isolated positive culture”) followed by at least two negative culture results at different visits (at least 7 days apart, without an intervening positive culture)
2. Women who become pregnant during treatment and stop their allocated treatment
3. Patients who died during treatment from violent or accidental cause (e.g. road traffic accident). N.B.: This does not include death from suicide, which will be considered an unfavourable outcome.
4. Patients who died during follow-up (after the end of treatment) with no evidence of failure or relapse of their TB, their last status being culture negative and their last positive culture result (“isolated positive culture”) followed by at least two negative culture results at different visits (at least 7 days apart), and who have not already been classified as unfavourable.
5. Patients who, after being classified as having culture negative status, are re-infected with a new strain from that with which they were originally infected. Reinfection will be defined specifically as a patient infected with a strain that is genetically different from the initial strain (see Mycobacteriology Laboratory Manual).
6. Patients who are able to produce sputum at 12 months, but whose 12-month visit sputum samples are all contaminated or missing, who cannot be brought back for repeat cultures, provided they have not already been classified as unfavourable and provided their last positive culture was followed by at least two negative cultures. N.B.: This does not apply to patients who are unable to produce sputum at 12 months, or to patients who are able to be brought back subsequently and produce negative cultures.

Patients in categories 1-5 above who had already been classified as having an unfavourable outcome will not be excluded.

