### **6.1.4. Unfavourable status in PP population**

1. Patients not classified as having achieved or maintained culture negative status when last seen, or
2. Patients previously classified as having culture negative status who, following the end of treatment, have two positive cultures without an intervening negative culture, (however, see Section 3.3 for an exception), or
3. Patients who had a positive culture not followed by at least two negative cultures when last seen, or
4. Patients dying from any cause during the 6 month treatment phase, except from violent or accidental cause (e.g. road traffic accident), not including suicide (e.g., suicide will be considered an unfavourable outcome), or
5. Patients definitely or possibly dying from TB related cause during the follow-up phase, or
6. Patients requiring a restart or a change of treatment because of an unfavourable outcome with or without bacteriological confirmation, i.e. on bacteriological, radiographic or clinical grounds

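### The PP death rule uses a 6-month window in every arm, against the arm-specific treatment period elsewhere; and MITT classifies week 17-26 deaths and losses differently in the control and the 4-month arms

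*SAP*

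**What the plan says.** **Treatment period.** SAP 3.1 says that it "is defined as either 4 or 6 months from start of therapy depending on allocated treatment regimen", with follow-up starting afterwards. SAP 3.4 sets the lengths at 119 and 182 days.

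**MITT, during treatment (6.1.3).** Item 4 makes unfavourable "Patients dying from any cause during treatment, except from violent or accidental cause". Item 8 adds "Patients lost to follow up or withdrawn from the study before the end of treatment". Section 4.4 repeats the loss rule, with month 4 or 6 as the cut-off.

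**MITT, after treatment (4.2).** Item 4 excludes "Patients who died during follow-up (after the end of treatment) with no evidence of failure or relapse of their TB", if culture negative. Item 1 excludes "Patients who, having completed treatment, are lost to follow-up or withdrawn from the study, their last status being culture negative". In both, any last positive culture must have been followed by two negatives, and patients already classified unfavourable stay in.

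**PP.** Section 4 builds PP from MITT by further exclusions. Item 1 of 4.3 removes losses before the end of treatment. Item 4 of 6.1.4 makes unfavourable "Patients dying from any cause during the 6 month treatment phase, except from violent or accidental cause", and does not limit this to the 6-month arms.

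**Decision.** Section 7 calls PP and MITT primary. It does not say that both must meet the 12% margin.

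**The concern.** There are two separate problems, both confined to comparisons 2 and 3 (a 4-month arm against the 6-month control). Comparison 1 sets 6 months against 6 months and is unaffected.

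First, the PP death rule conflicts with the definition of the treatment period and with the MITT exclusions that PP inherits. Two programmers could code a primary analysis differently, and each could cite the SAP.

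Second, the MITT rules attach a different outcome to the same event at the same time since the start of therapy, depending on the arm. If such events are equally frequent, the control gains unfavourable outcomes that the 4-month arm does not. That moves the difference towards non-inferiority in the two comparisons that test shortening. Section 4.4 gives a reason for excluding late losses and non-TB deaths, but none for a death cut-off that differs by arm.

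**Working it through.** **1. The text, event by event.** Take a patient who is culture negative, with no evidence of failure or relapse, and has an event between day 119 and day 182. A 4-month patient has completed treatment.

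| Event | Control (6 months) | 4-month arm |
|---|---|---|
| Non-TB, non-violent death, MITT | unfavourable (6.1.3 item 4) | excluded (4.2 item 4) |
| Loss or withdrawal, MITT | unfavourable (6.1.3 item 8) | excluded (4.2 item 1) |
| Non-TB, non-violent death, PP | unfavourable (6.1.4 item 4) | excluded (4.2 item 4, through section 4) or unfavourable (6.1.4 item 4) |
| Loss or withdrawal, PP | excluded (4.3 item 1) | excluded (4.2 item 1) |

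The clause in 4.2 that keeps patients already classified unfavourable does not settle the third row: whether the death is itself such a classification is the open question. The PP conflict concerns deaths only.

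**2. The plan's own figure.** Appendix 1 assumes 16% unfavourable, a 12% margin, 90% power, 2.5% one-sided, 15% unassessable and 8% isoniazid mono-resistant. Then 2 × 0.16 × 0.84 × (1.960 + 1.282)² / 0.12² = 196.1, and 196.1 / (1 − 0.15 − 0.08) = 254.7, which rounds up to the stated 255. The sample size is not at issue. With 300 recruited, 300 × 0.77 = 231 analysed per arm.

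**3. Shift in the MITT difference.** Let x be the share of each arm with a week 17-26 event of this kind, counted inside the unfavourable rate. The SAP does not give x, so every value is an assumption. Under equal truth the control shows 0.16 and the 4-month arm shows (0.16 − x)/(1 − x).
- x = 0.5%: 0.155/0.995 − 0.16 = −0.42 points
- x = 1%: 0.15/0.99 − 0.16 = −0.85 points

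**4. MITT read alone at the margin.** The true rates are 16% and 28%, with an unstratified Wald interval. The 4-month arm shows (0.28 − x)/(1 − x) on 231(1 − x) patients.
- x = 0.5%: rate 27.64%, difference 11.64 points, SE 3.81 points. Error = Φ(0.36/3.81 − 1.96) ≈ 3.1%; simulation gives 3.2%.
- x = 1%: rate 27.27%, difference 11.27 points, SE 3.81 points. Error = Φ(0.73/3.81 − 1.96) ≈ 3.8%; simulation gives 3.9%.

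**5. PP and MITT both required (simulation).**
- Losses alone at 0.5, 1, 2 and 3%: error 2.5, 2.4, 2.2 and 2.1%. There is no inflation, because PP drops these patients in both arms.
- Deaths alone at 0.5%, with 4.2 item 4 governing and PP otherwise identical to MITT: 3.2%. If 6.1.4 item 4 governs: 2.5%.
- The same deaths, with further patients who are unfavourable in MITT but dropped from PP (assumed 0.5% window losses and 2% others; 1% and 4%; 1% and 8%): 2.3, 1.9 and 1.1%. These place the 12-point difference in MITT. Placed in PP, the same cases give 2.8, 2.8 and 2.7%.

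**6. How often the PP coding decides.** At 0.5% deaths the two codings give opposite PP verdicts in 1.5% of trials under equal truth, and in 4.8% at a true difference of 5 points. For illustration, with control 37/231, a 4-month arm at 49/231 has upper limit 12.3% if its one such death counts, and at 48/230 has 11.9% if it is excluded.

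**7. Is 0.5% plausible for deaths?** The IUATLD study cited in 4.4 had 42 deaths among 1044 + 311 = 1355 patients, or 3.1%. Spread evenly over an assumed 78 or 52 weeks, nine weeks give 3.1% × 9/78 = 0.36% or 3.1% × 9/52 = 0.54%. The SAP gives no cause, timing or culture status for those deaths, so the share meeting 4.2 item 4 could be lower.

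**The case against.** **Arm-specific periods are a stated choice.** Sections 3.1, 3.4 and 4.4 use them openly, and one phrase in 6.1.4 departs from them. On this view PP nesting removes the 4-month patient first and a one-line correction is enough. It stands that such a correction would remove the contradiction. It would also leave both primary analyses arm-dependent for deaths, so the choice needs a stated reason.

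**The trial's decision error may not be inflated.** A reader might infer that the false-positive rate of the trial exceeds 2.5%. The documents do not support this if both primary analyses must pass. Losses then cause no inflation. The 3.2% for deaths requires PP and MITT to be otherwise identical, whereas 4.3 drops patients whom 6.1.3 counts as unfavourable. Section 2 expects true control failure and relapse of 3% to 5%, against the 16% unfavourable assumed in Appendix 1. This objection stands.

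**Larger figures need larger rates.** MITT alone reaches 5.9% or 8.7% only with 2% or 3% of patients having such an event within nine weeks. Nothing in the SAP supports that for deaths.

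**The calculations simplify.** They ignore the stratification and the gatekeeping in section 7, and the one-patient example sits at the boundary by construction. Both remarks are fair; the conflict in the text does not depend on them.

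**Safeguards exist.** ITT counts all these patients as unfavourable in every arm. Sensitivity analyses 2 to 4 treat missing ITT outcomes alike across arms, and analysis 6 equalises deaths in MITT and PP. This stands in part: section 7 allows some of these to miss the margin, none decides which PP coding is primary, and none equalises losses within MITT.

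**Conclusion.** The contradiction between 6.1.4 item 4 and sections 3.1, 3.4 and 4.2 item 4 is certain from the text and should be resolved before database lock. The MITT asymmetry in comparisons 2 and 3 is also certain from the text; under equal event rates it favours the 4-month regimens.

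Its size is uncertain, because every week 17-26 rate is assumed. Each 1% of patients moves the MITT difference by about 0.85 points. If both primary analyses must pass, error with about 0.5% deaths ranges from about 3.2% to below 2.5%, depending on how far PP and MITT differ.

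A reader might also infer that 26 weeks is the correct primary window for deaths. The documents do not establish that: 4.2 item 4 and the reasoning in 4.4 point towards excluding non-TB deaths after completed treatment. What is wrong is that the SAP applies two windows without choosing. This should be fixed, but it does not undermine the design.

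**What to change.** 1. Before database lock, reconcile 6.1.4 item 4 with 3.1, 4.2 items 3 and 4, and 6.1.3 item 4, so that one stated window classifies deaths in both PP and MITT. A common 26-week window or the arm-specific period would each remove the contradiction. If the arm-specific period is kept, state the reason and report sensitivity analysis 6 beside the primary result for comparisons 2 and 3.
2. Keep the primary rule for losses. Add to section 8 one MITT sensitivity analysis of comparisons 2 and 3 in which losses, withdrawals and non-violent deaths up to week 26 are classified alike in every arm.

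The cost is a few lines of SAP text and one more run of an existing analysis. Under a common window, a few non-TB deaths in the 4-month arms would become unfavourable.
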